After study completion, any future release of data collected will be contingent upon the repository guardian verifying a separate full IRB approval for each specific human subject research activity that uses identifiable repository data. The repository guardian will be personally responsible for verifying that future releases of data are done in concordance with pre-proposed limits and the original consent. Data transport at the time of any potential future IRB approved data sharing will be clarified and approved at the time of data by submission of an updated Repository Sharing Agreement and separate IRB approval. Any updated data requests and Repository Sharing Agreements will be stored alongside study data in the Red Cap repository in a separate file entitled "Repository Sharing Agreements and External Data Requests." This will be maintained and tracked by [name]. External researchers will be required to use the Red Cap repository for all data storage, therefore data transfer will not be necessary and data security ensured.

No data submittal from outside sources is expected.

8. Data Analysis

- 1) For primary endpoint: descriptive analysis and chi-squared test for comparative analysis
- 2) For secondary endpoints:
 - Descriptive analysis
 - Explore bivariate and multivariate associations between psychosocial factors computed through scales (e.g., stigma, social support, quality of life) and (a) treatment readiness at baseline, (b) treatment outcomes [SRV, biological outcomes, etc.] at 12 months, (c) re-infection (or SRV) at 48 months. Demographic controls will include age, education, work status, and relationship status.
 - Conduct constant comparative qualitative analysis of focus group and individual discussions using Atlas.ti software. The domains of analysis will include lived experiences with stigma, discrimination, positive and negative social support systems, and risk management. Emergent themes and domains identified through qualitative analysis will result in a richer understanding of factors that contribute to implementing successful treatment for people who currently use drugs.

In addition to the above, mixed methods data will comprise biological data, psychosocial data collected via questionnaires, and qualitative narrative data from transcribed in-depth interviews.

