Analytic across-case analysis entails comparative analysis, distinguishing between groups of people who exhibit different behavioral patterns. This allows the investigators to go beyond simple assertions about majority and minority patterns and to make analytic—as opposed to descriptive—statements about how certain values or behaviors relate to broader psychosocial and institutional factors.

Power/Sample Size:

Based upon a sample size of n=50 subjects in the combined safety net/needle exchange clinics and 50 subjects in the retrospective comparator group, this study has 80% power to detect a 20% difference between groups; this calculation is based on the assumption that the retrospective comparator group will have and SVR12 rate of 95% (taking into account treatment discontinuation and relapse rates, i.e. intention to treat analysis) compared to SVR12 rate of 70% in the safety net clinic patients.

In the intervention group (safety net clinics) a total of 50 subjects will be enrolled to allow for a 10% attrition and loss to follow up.

9. Privacy, Confidentiality, and Data Security

All data will be collected and entered in a private, clinical care environment, behind closed doors. All study collaborators with access to personal data, de-identified or not, will be required to undergo full OHSU IRB training.

At Old Town Clinic, subjects will be recruited as described in Section 5e. There will be limited risk of a privacy violation with this method. The consent process will be performed during the course of a clinical visit, in an exam room, one-on-one with the site coordinator.

At Outside In, subjects will be recruited as described in Section 5e. There will be limited risk of a privacy violation with this method. The consent process will be performed after a clinical visit in a private office in the syringe exchange, one-on-one with the site coordinator.

At all sites, laboratory and/or imaging tests, clinical visits, dispensation of medications, and communication of test results will be performed in concordance with HIPPA appropriate clinical care. All surveys and qualitative data will be collected in a private space, such as an exam room or meeting room behind closed door.

For more details, please see section 7c above.

10. Provisions to Monitor the Data to Ensure the Safety of Subjects

See DSMP document, attached.

9. Risks and Benefits a. Risks to Subjects

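### The power statement claims a 20% difference, but its own SVR12 rates (95% and 70%) are 25 points apart, and the stated 80% power fits about 20 points at an assumed two-sided 5%

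*Combined protocol and SAP*

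**What the plan says.** The Power/Sample Size paragraph at the end of section 8 (Data Analysis) takes "n=50 subjects in the combined safety net/needle exchange clinics and 50 subjects in the retrospective comparator group" and states that "this study has 80% power to detect a 20% difference between groups". The same sentence gives the rates behind the calculation. For the comparator it assumes an "SVR12 rate of 95% (taking into account treatment discontinuation and relapse rates, i.e. intention to treat analysis". The second rate, for the two prospective sites together, then follows as the contrast: "compared to SVR12 rate of 70% in the safety net clinic patients".

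The next sentence adds that in the intervention group "a total of 50 subjects will be enrolled to allow for a 10% attrition and loss to follow up".

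The test is named at the start of section 8: "For primary endpoint: descriptive analysis and chi-squared test for comparative analysis". The plan does not state a significance level, whether the test is one- or two-sided, or whether a continuity correction applies. It gives no other power or sample-size calculation.

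**The concern.** A difference of 20% and rates of 95% and 70% cannot both describe the planning assumption. The rates are 25 points apart, and 20% is not their relative difference either. The 80% power might have shown which figure is the slip, so it has to be recomputed under both readings.

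What is at stake is how the result will be read. The primary objective is to show that SVR12 in the safety-net sites is similar to that in the hepatology clinic. If the chi-squared test is not significant, its meaning depends on how large a gap the trial could have found. On the pooled approximation below, a true 20-point gap would be missed about 19% of the time and a true 25-point gap about 8% of the time. The plan leaves open which gap it was sized for.

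**Working it through.** **Inputs.** From the Power/Sample Size paragraph: n = 50 per group, comparator rate p1 = 0.95, safety-net rate p2 = 0.70, stated difference 20%, stated power 80%. From section 8: chi-squared test. Assumed, because the plan does not give it: two-sided α = 0.05, so z = 1.96.

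**Step 1. The difference (no assumption needed).**
- Absolute: 95 − 70 = 25 points.
- Relative: 25/95 = 26.3%.
- A 20-point drop from 95% is 75%. A 20% relative drop is 0.80 × 95 = 76%. Neither is 70%.

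**Step 2. Try to reproduce the 80% at the printed rates.** The pooled normal approximation is

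power = Φ{ [(p1 − p2) − z·√(2·p̄(1 − p̄)/n)] / √([p1(1 − p1) + p2(1 − p2)]/n) }, with p̄ = (p1 + p2)/2.

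For 95% vs 70%, p̄ = 0.825:
- null standard error √(2 × 0.825 × 0.175/50) = 0.0760
- alternative standard error √((0.0475 + 0.2100)/50) = 0.0718
- (0.25 − 1.96 × 0.0760)/0.0718 = 1.41, so power = 92.0%

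The stated 80% is not reproduced.

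**Step 3. Same formula with a 20-point gap.** For 95% vs 75%, p̄ = 0.85:
- null standard error √(2 × 0.85 × 0.15/50) = 0.0714
- alternative standard error √((0.0475 + 0.1875)/50) = 0.0686
- (0.20 − 1.96 × 0.0714)/0.0686 = 0.88, so power = 80.9%

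This matches the stated 80%. For comparison, a 20% relative drop (95% vs 76%) gives 77.8%, and keeping 70% with a 20-point gap (90% vs 70%) gives 71.1%.

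**Step 4. Other methods, 50 vs 50, two-sided 5%.** The continuity-corrected approximation subtracts ½(1/50 + 1/50) = 0.02 from the difference. The exact rows sum binomial probabilities over all tables that the test rejects. The last column is the gap below 95% that has 80% power.

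| Method | 95 vs 70 | 95 vs 75 | Gap with 80% power |
|---|---|---|---|
| Pooled approximation | 92.0% | 80.9% | 19.7 points |
| Unpooled approximation | 93.6% | 83.1% | 19.0 |
| Arcsine | 94.3% | 84.6% | 18.5 |
| Continuity-corrected approximation | 87.1% | 72.0% | 22.3 |
| Exact, uncorrected chi-squared | 94.8% | 85.2% | 18.3 |
| Exact, continuity-corrected chi-squared | 89.9% | 74.8% | 21.4 |

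For 95 vs 75 the methods fall on both sides of 80%. For 95 vs 70 all of them exceed it by at least 7 points.

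**Step 5. Sensitivity to the assumed α (two-sided).**

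| α | 95 vs 70, pooled | 95 vs 75, pooled |
|---|---|---|
| 10% | 95.9% | 88.6% |
| 5% | 92.0% | 80.9% |
| 2% | 84.6% | 68.9% |
| 1% | 77.5% | 59.3% |

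Pooled power at 95 vs 70 falls to 80% only at α of about 0.0126, a level the plan does not mention.

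**Step 6. Attrition.** If 10% of the 50 safety-net subjects are lost, 45 remain. At 50 vs 45 and two-sided 5%, pooled power is 90.7% for 95 vs 70 and 79.2% for 95 vs 75. The pattern does not change.

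**The case against.** Nobody can defend the 20 against the 25. The stronger objection is that the 80% cannot show which number is wrong, because it depends on a significance level and a formula that the plan does not state.

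- With the continuity-corrected approximation at two-sided 5%, power at 95 vs 75 is only 72.0%, and the gap with 80% power is 22.3 points, not far from midway between 20 and 25.
- At two-sided 2.5%, which a split over the two listed primary endpoints (SVR12 and SVR48) would give, that formula yields 79.7% for 95 vs 70.
- Sizing 95 vs 70 for 80% power at two-sided 5% with the continuity correction needs 43 per group, and 43/0.9 = 47.8, so 48 after 10% attrition, close to the 50 enrolled. A 25-point gap may therefore have been the planning value.
- The effect is also small: the study calls itself a pilot, the group sizes are fixed, and no analysis decision uses the power figure.

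Much of this stands. The documents do not show whether the 20 or the 70 is the slip, and the fit to 20 points is conditional. But the 2.5% level appears nowhere in the plan, and section 7 names a single primary outcome. The sizing route does not rescue the sentence, because the sentence claims 80% at 50 vs 50, where the continuity-corrected figure is 87.1%. Attrition is not decisive either, since the rates are described as intention to treat, so subjects lost to follow-up may still count among the 50. None of these readings makes 95 minus 70 equal to 20.

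**Conclusion.** The point holds. The contradiction between a 20% difference and rates of 95% and 70% is plain arithmetic and rests on no assumption.

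The second part is conditional on a two-sided 5% test. There, every method tried puts power at the printed rates between 87.1% and 94.8%, and the gap detectable with 80% power between 18.3 and 22.3 points. The stated 80% therefore lies nearer to 20 points than to 25. This describes the fit; it does not prove which figure was intended.

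At the printed rates the statement understates power, so the error conceals no shortfall there. It should be fixed because it is the only account of the trial's detectable difference. It does not threaten the design.

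**What to change.** The sponsor should state which safety-net SVR12 rate the calculation used and replace the power sentence with one that is internally consistent and names the significance level, the chi-squared variant and the method. If two-sided 5% is confirmed, one of these would serve:

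> With 50 vs 50 subjects and a two-sided 5% chi-squared test [variant], power is about 81% for SVR12 of 95% vs 75% (20 points), by the pooled normal approximation.

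> With 50 vs 50 subjects and a two-sided 5% chi-squared test [variant], power is about 92% for SVR12 of 95% vs 70% (25 points), by the pooled normal approximation.

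If exact power is preferred, the figures are 85.2% (20 points) or 94.8% (25 points) for the uncorrected test, and 74.8% or 89.9% with the continuity correction. It would help to add whether subjects lost to follow-up stay in the 50 as non-responders, so that the attrition sentence agrees with the sample size in the power sentence.

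The cost is wording in one paragraph. Enrolment, endpoint and test stay as they are.

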Another unique offering at OTC is fully integrated Alcohol and Drug treatment services within primary care. We offer level 1 outpatient treatment for individuals suffering from opioid use disorder and others who suffer from comorbid chronic pain and substance use disorders. We have a robust medication assisted treatment program housed within primary care. Specifically, we offer buprenorphine and longacting naltrexone in conjunction with mandatory group and individual counseling sessions. These patients are some of the most adherent of the OTC population because the A&D program requires this (i.e. twice weekly groups, weekly medication dispensing, etc.). This population (i.e. PWIDs or have a history of IVDU) is disproportionately affected by HCV, so having this recovery support will not only improve treatment adherence but will reduce the risk of HCV re-infection.

The overall goal of OTC's HCV treatment program is to improve the care of its patients suffering from chronic Hepatitis C virus and to standardize the screening, diagnosis, work-up, and treatment of this condition throughout OTC. Patient-centered design is at the core of the creation of this program. Patient and provider co-design, utilizing human-centered design principles and tools, has been central to its development.

Essential parts of OTC's program include referral by the primary care provider (PCP), initial office visit and assessment with an OTC HCV provider, weekly medication dispensing, bi-weekly clinical pharmacist visits, monthly lab monitoring, referral to medication assisted treatment or mental health services as indicated, and optional participation in education and peer support sessions. These sessions will be initially modeled after previously validated peer support groups for treatment with interferon-based regimens,^{3,5} and further refined through our iterative, human-centered design process. Patients who are recent (previous 12 months) or current injection drug users will be strongly encouraged, but not required, to meet weekly in groups of less than 12 individuals, facilitated by certified drug and alcohol counselors. Patients electing to attend HCV health education sessions will partake in a 1 hour, certified health educator-lead, interactive hepatitis C education session, focusing on medical and social aspects of the disease, adherence, and re-infection prevention. [Integrative HCV Treatment Model At Two Study Sites](#)

Outside In HCV Treatment Program

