Mental health is fully integrated into our primary care services. Psychiatric nurse practitioners and licensed clinical social workers on each care team offer diagnosis and management recommendations as well as counseling services. For patients suffering from severe and persistent mental illness, OTC coordinates care with a co-located specialty mental health program that offers more intensive behavioral health support including case management.

OTC has fully integrated Alcohol and Drug treatment services within primary care. They offer level 1 outpatient treatment for individuals suffering from opioid use disorder and others who suffer from comorbid chronic pain and substance use disorders. Because of this, these patients are some of the most adherent of the OTC population because the A&D program requires this (i.e. twice weekly groups, weekly medication dispensing, etc.).

e. Recruitment Methods, by site, estimated to take 2-3 months.

Old Town Clinic. Upon study initiation, the site principle investigator will pull a list of active patients in the Old Town Clinic buprenorphine-based Medication Assisted Program who also carry a diagnosis of chronic hepatitis C. In addition, patients requiring level 2 intensive outpatient substance use treatment receiving methadone or buprenorphine-based Medication Assisted Therapy with co-morbid chronic hepatitis C will be pulled by chart study coordinator chart review. Anyone not meeting the inclusion criteria or with automatic exclusion criteria will be excluded. The study coordinator will then contact the remaining patients in a sequential fashion via telephone with the following script: "Hello I'm _____ a _____ at Old Town Clinic. We are looking for patients in the Suboxone program at Old Town interested in treating their hepatitis C. We cannot guarantee it without a doctors visit, but we may be able to treat your hepatitis C. Would you like to make an appointment to be screened?" We will also post fliers in the meeting rooms stating, "Are you Hepatitis C Positive? Are you interested in treatment? Old Town Clinic is part of a study working to treat people with HCV. For more information and to see if you qualify for this study, please call 971-XXX-XXXX". The first 25 patients that agree to be screened, meet criteria, and sign an informed consent to enroll in the study will be enrolled. Subjects will be reimbursed for each survey or in-depth interview with a \$15 Fred Meyer gift card.

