Outside In. Upon the study initiation, Outside In's Injection Drug Users Health Services Program will begin handing out fliers to all clients of the syringe exchange program as well as posting fliers on the bulletin board in the waiting room. These fliers will read, "Are you Hepatitis C Positive? Are you interested in treatment? Outside In is part of a study working to treat people with HCV. For more information and to see if you qualify for this study, please call 503-535-XXXX". This outreach process will be augmented with a respondent-driven sampling method called "snowball sampling," which uses social networks to find more clients in hard to reach populations. Representative seed subjects will be given

three coupons (fliers) to be given to other syringe exchange clients who also might be treatment candidates. Subjects may also be referred to study by their Outside In primary care provider. The phone line will be answered by the site coordinator and will have a voicemail that says “Thank you for your interest in our study. For this study, you need to be a current injection drug user. You must be over the age of 18. Please leave a name and a phone number you can be reached at. All calls will be returned the morning of the next business day. Thank you for your interest.” The site study coordinator will return the client’s call (two attempts will be made). This staff will confirm the initial screening conditions, inquire about insurance status, and make a medical appointment if appropriate. If the client is uninsured, he/she will be directed to OHP (Oregon Medicaid) enrollment and asked to re-engage with the study when insurance is active. If the client is insured by OHP, an appointment will be made for the client to meet with a treating medical provider. The provider appointment will serve as a medical screening visit to include missing baseline lab testing necessary to determine eligibility, the results of which will be helpful in determining inclusion. The first 25 patients that agree to be screened, meet criteria, and sign an informed consent to enroll in the study will be enrolled. Subjects will be reimbursed for each survey or in-depth interview with a \$15 Fred Meyer gift card.

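### At Old Town Clinic, the fixed recruitment call script names the Suboxone programme and hepatitis C with no check on who has answered, yet the privacy section rates the method's risk as limited.

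*Combined protocol and SAP*

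**What the plan says.** Section 5e (Recruitment Methods) describes how Old Town Clinic finds its subjects. The site investigator lists patients in the clinic's buprenorphine programme "who also carry a diagnosis of chronic hepatitis C". Chart review adds patients in more intensive outpatient treatment who receive methadone or buprenorphine and also have hepatitis C. People who fail the criteria are removed, and then: "The study coordinator will then contact the remaining patients in a sequential fashion via telephone with the following script". After blanks for the caller's name and role, the script continues "at Old Town Clinic. We are looking for patients in the Suboxone program at Old Town interested in treating their hepatitis C". Its next sentence adds, with a caveat about needing a visit first, that "we may be able to treat your hepatitis C". It ends by offering a screening appointment.

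The section headed Privacy, Confidentiality, and Data Security refers to section 5e for Old Town Clinic recruitment and concludes: "There will be limited risk of a privacy violation with this method". It gives no reason and does not mention the telephone call. The same sentence appears again for Outside In. This point concerns only its first appearance, for Old Town Clinic.

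**The concern.** The privacy rating applies to a method whose wording is fixed in the protocol, and that wording opens with sensitive information. If a relative, housemate, shelter worker or new holder of the number answers, the first substantive sentence links someone reached at that number to a Suboxone programme and to hepatitis C.

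The call comes before consent, so those exposed include people who are never screened, decline or turn out to be ineligible. The protocol itself treats stigma as important: section 6 administers a scale of anticipated stigma related to chronic illness, and the interview guide asks about stigma and discrimination linked to hepatitis C. An avoidable disclosure during recruitment is the kind of harm that these instruments are meant to study. At stake is the protection of people approached for the study, not the validity of its results.

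**Working it through.** No arithmetic applies. The check sets the call procedure against the privacy rating and then looks for a safeguard elsewhere.

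1. **Who is called.** By construction, everyone on the list receives or is enrolled in medication-assisted treatment and has chronic hepatitis C (section 5e). What a listener would infer from the script is therefore true of the person being called.

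2. **What is said, and in what order.** The script runs: greeting; caller's name, role and clinic; the Suboxone programme and hepatitis C together ("We are looking for patients in the Suboxone program at Old Town interested in treating their hepatitis C"); then hepatitis C attributed to the listener ("we may be able to treat your hepatitis C"). It does not ask for the patient by name, confirm who has answered or ask whether the person is free to talk. It has no branch for a third party or an answering machine.

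3. **What the programme name conveys.** Section 5d describes the clinic's alcohol and drug services with the words "We offer level 1 outpatient treatment for individuals suffering from opioid use disorder" and places buprenorphine in the medication-assisted programme within primary care. The script therefore states one diagnosis outright and implies treatment for opioid use.

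4. **Whether another section covers the call.**
   - The privacy section protects data entry, consent, surveys and interviews by requiring private rooms. These safeguards apply after the patient has come to the clinic.
   - Its HIPAA sentence covers tests and imaging, visits, dispensing and test results. Recruitment calls are not listed.
   - Its cross-reference to section 7c leads to data and specimen banking, which has no telephone procedure.
   - The list of risks to subjects covers questionnaires, blood draws and treatment. It does not mention disclosure during recruitment.
   - Section 5f deals with consent at the intake appointment, which follows the call.

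5. **Result.** The written method contains a route by which sensitive information can reach the wrong person. The section that rates the method neither mentions that route nor gives a control for it.

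**The case against.** The best defence is that the script is recruitment wording for use once the patient is on the line, not a full call procedure. It contains no patient name and no request to speak to anyone, which fits that reading, and silence on identity is not an instruction to disclose to others. The callers are clinic employees with access to the medical record, contacting the clinic's own patients, and collaborators with access to personal data must complete IRB training. The privacy section also says the risk is limited, not absent.

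Much of this is fair. Staff may well verify identity in practice, and this is not unsolicited contact by strangers. But none of these features is a control on the call, and the protocol gives the script as the method whose risk it rates. A reader can assess only what is written, and writing in a check that staff already make would cost almost nothing.

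A reader might infer that the Outside In voicemail has the same defect, because it says "For this study, you need to be a current injection drug user" and then asks for a name and number. The documents do not support that. Clients ring that line themselves after seeing a flier, the site coordinator answers it, and any message left goes to study staff. That is a volunteer giving information to the study, not the study disclosing it to whoever picks up. Removing the sentence would only move the question to an outbound return call, for which no identity check is described either.

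**Conclusion.** The point stands for Old Town Clinic alone. As written, the script can disclose hepatitis C and, by implication, opioid-use treatment to someone other than the patient before consent, and the privacy rating does not address this.

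Its size cannot be stated. The documents do not say how many calls will be made to enrol the 25 subjects, how often someone else answers, or whether phones are shared. A reader might take the statement in section 5d that more than 70% of the clinic's patients are homeless as grounds for an estimated number of disclosures. That figure describes the whole clinic, not the call list, and says nothing about telephones. Nor does the script disclose two named diagnoses: it names one condition and one programme, and a third party must still infer whom it concerns.

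The conclusion assumes that the script is used as printed, with no unwritten check before it. It does not show that the word limited is false, only that the protocol gives nothing to support it for this call. No endpoint, sample size or analysis is affected. It is a small correction to the wording, worth making because it protects people who have not agreed to take part.

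**What to change.** In section 5e, reword the Old Town Clinic script so that the coordinator:

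- asks for the patient by name;
- confirms identity;
- confirms that the patient can talk; and
- only then mentions the programme, the study or hepatitis C.

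Add a rule that anyone else who answers, or a voicemail, receives only a neutral request to call back, with no programme or condition named. Then revise the Old Town Clinic sentence in the privacy section so that its risk statement refers to this safeguard.

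The cost is a slightly longer call and a minor IRB amendment. No extra staff or data are needed, and eligibility, endpoints and analysis stay as they are. This point calls for no change to the Outside In recording.
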